#### **4.2.2 Rationale for Dose Selection/Regimen/Modification**

In the previous hematologic phase I study (OTX015\_104 / MK-8628-001), a dose escalation was completed and preliminary results of the cohort expansion are available. As of June 2015, a total of 87 subjects had been included in the dose escalation part in the two cohorts (AL and OHM), and a further 49 subjects had been included in three dose expansion cohorts. A QD schedule was evaluated at all levels (up to 160 mg) and a 40 mg BID schedule was also evaluated.

The preliminary RD for the QD schedule was 80 mg QD, with a 14 days ON/7 days OFF schedule for both the OHM and the AL cohorts. DLT of thrombocytopenia was the prevalently observed AE in the OHM cohort, occurring above 40 mg QD. At DL4, thrombocytopenia was more frequent at 40 mg BID with a higher incidence of thrombocytopenia compared to the equivalent total dose per day given as QD, i.e., 5/6 subjects vs. 2/7 subjects, respectively - making the dose of 40 mg BID unacceptable with >33% of DLT in this cohort. The main limiting toxicities reported are thrombocytopenia, fatigue, gastrointestinal toxicities, as well as asymptomatic bilirubin increases and Factor VII decreases.

Preliminary clinical activity has been observed at a range of dose levels, including objective responses at 40 mg QD (1 CR), 80 mg (CRI) and 160 mg (CR) in the AL cohort and at 80 mg QD (1 PR) and 120 mg (2 CR) in DLBCL subjects.

A total of 49 subjects had been treated in the expansion cohorts with non-continuous dosing at 80 mg QD, 14 days ON/7 days OFF: 16 AML post-MDS subjects, 18 AML non-MDS related (i.e. de novo, secondary to chemotherapy or MPD) subjects, and 15 DLBCL subjects. The expansion cohort demonstrated that at 80 mg QD, 14 days ON/7 days OFF was reasonably well tolerated with no DLTs reported. However, one subject with AML had grade 3 asthenia, deemed not related by the investigator after clarification (related to aspergillosis), and one subject with AML had a dose reduction due to poor tolerance (asthenia, anorexia, dysgeusia G2).

In the dose expansion cohort, one PR has been reported to date in a DLBCL subject along with evidence of clinical activity not yet meeting standard response criteria in some ongoing subjects (decrease in bone marrow blasts in five AML subjects and decreased lymph node lesions in two DLBCL subjects).

##### **4.2.2.1 Starting Dose for This Trial**

Data is now emerging on how to better dose epigenetic therapies, including more frequent dosing that avoids undesirable effects mediated by higher concentrations and resultant enhanced broad inhibition of the targeted genes. The limited number objective responses in

the dose expansion cohorts in the hematologic malignancies study where MK-8628 was given in a discontinuous manner (i.e. 14 days ON/7 days OFF) raises the question of whether there is a need for continuous and sustained target inhibition. On the basis of several translational and clinical studies, low, prolonged drug exposure is becoming the hallmark of successful epigenetic modulation [40]. Notable epigenetic agents where this phenomenon is observed include FDA-approved DNMT inhibitors such as 5-azacitidine and decitabine [41]. Clinical development of these agents was initially hindered because early trials used higher, infrequent doses that proved to be substantially toxic to subjects (likely because of off-target epigenetic modulation). Lower, continuous dosing was found to markedly decrease treatment-related AEs and enhance targeted effects on DNA methyltransferases because the concentrations are maintained at a level where cytotoxic effects are not the prevailing mode of action. The available data support the notion that maintaining concentrations that avoid immediate cytotoxic effects but engage the target in a continuous fashion allows for reprogramming of the tumor cells that can alter disease biology in a durable, clinically meaningful manner [40].

Therefore, to maintain or sustain target inhibition with MK-8628 and mitigate daily fluctuations in systemic concentrations, a more frequent dosing schedule will be evaluated in this protocol using BID dosing. The hypothesis underlying this approach is that a higher Ctrough achieved with lower, more frequent dosing may be needed to disrupt super-enhancer driven oncogene expression (e.g., Myc, Bcl-2) over longer periods of time in order to induce antitumor activity [38]. Enhanced preclinical efficacy seen with the BET inhibitor JQ1 and MK-8628 with more frequent dosing (BID versus QD) seen in preclinical evaluations [26][38][42] is likely attributable to the ability of these powerful gene expression enhancers to quickly restore oncogene expression once the compound exposure wanes. Considering the short half-life for MK-8628 of ~5-6 hours, BID dosing has the potential to maintain sustained target engagement at a lower dose (i.e. lower Cmax could help avoid off-target toxicities).

Based on available PK data and results suggesting MK-8628 exhibits dose proportional exposure and a half-life much shorter than either a 12-hour or 24-hour dosing interval, a Ctrough 12 hours after BID dosing will more than likely result in significantly higher concentrations than a Ctrough of double the same dose at 24 hours (~4 cumulative half-lives). For example, the MK-8628 PK results from both cohorts combined shown in Figure 1 demonstrate that a 40 mg BID dose attains significantly higher Ctrough than a similar daily dose of 80 mg QD. In the absence of a clear understanding of target engagement at different doses and an appropriate efficacious dose, total daily doses up to 60 mg administered as BID (i.e., max of 30 mg BID) or additional dose schedules will be evaluated with the hypothesis that more frequent dosing may improve efficacy.

Because epigenetic reprogramming can take longer to become apparent than the actions of traditional chemotherapies, a continuous prolonged course of treatment may be required for efficacy evaluation. Balancing this against risk (thrombocytopenia) and tolerability issues (as seen in the initial dose escalation), a lower, more frequent BID dosing schedule will be explored primarily for Proof of Concept (POC).

In [Figure 2](#) below, PK comparison of QD versus BID in the combined dose escalation cohorts suggests that Ctrough or time above threshold could underlie hematologic toxicity and potentially efficacy of MK-8628. PK data suggest no difference in total exposure (top graph).

Median daily AUC of 40 mg BID is similar to 80 mg QD. However, there is a large difference in median trough concentration (bottom graph).

[figure not shown]

Figure 2 PK comparison of QD versus BID

#### 4.2.2.2 Maximum Dose/Exposure for This Trial

The maximum dose for the BID regimen in this study will be the highest dose level tolerated (< 25% DLT rate).

#### 4.2.2.3 Rationale for Dose Interval and Trial Design

The purpose of this trial is to determine the recommended phase 2 dose (RP2D) of MK-8628 for further phase II trials in subjects with selected hematologic malignancies that might benefit from BET inhibition. The RP2D of BID administration regimens will be explored using a 6+8 two-stage design which offers a fast approach with continuous DLT rate monitoring via a modified toxicity probability index (mTPI)(Ji design)[1].

### 4.2.3 Rationale for Endpoints

#### 4.2.3.1 Safety Endpoints

##### 4.2.3.1.1 Primary Safety Endpoint:

A primary objective of this trial is to determine the recommended phase II dose (RP2D) of MK-8628. Selecting the RP2D will involve a multi-faceted decision taking into account safety, tolerability, early efficacy signal, PK exposure and PD markers. The primary endpoint driving dose selection is the DLT rate, with weight given to the highest DL tolerated (< 25% DLT rate). All other facets will be considered supportive. It is important to note that dose selection in this study aims to assess a recommended phase 2 dose *range*, with other factors aside from those mentioned above, such as target engagement, contributing to refining the dose selection for phase 2. This will be further evaluated in subsequent clinical investigations in either monotherapy or combination trials.

#### Secondary Safety Endpoints

The secondary safety endpoint will be to evaluate the safety and tolerability of MK-8628 across subjects with AML (de Novo and post-MDS) and DLBCL included in this trial. Safety will be assessed in subjects who have received MK-8628 by determining the RP2D and quantifying and grading reported AEs using CTCAE, Version 4.0. Attribution to drug, time-of-onset, duration of the event, resolution, and any concomitant medications administered will be recorded. AEs to be analyzed include but are not limited to all AEs, ECIs, SAEs, fatal SAEs, and laboratory changes.

#### 4.2.3.2 Pharmacokinetic Endpoints

Plasma parameters of MK-8628 as appropriate and according to analyses performed (non-compartmental or nonlinear mixed effect modelling) will be determined and may include trough (Cmin) and peak (Cmax) concentrations, Tmax, AUC[0-∞], Vdss, t1/2, steady state, total clearance (CL). PK data for MK-8628 will be interpreted in terms of safety findings and compared with historical data. Incidence and severity of AEs along with PK parameters will be analyzed in relation to the most pertinent biomarker(s), if any.

#### Pharmacodynamic Endpoints

Inhibition of BET proteins by MK-8628 leads to alterations in the transcription of mRNA at loci most sensitive to disruption of BET activity. These are considered target genes. Changes in expression, measured via mRNA, of prespecified target genes\* will be used as PD biomarkers to assess target engagement of BET proteins by MK-8628. (\*Note: the following non-exhaustive list of target genes may be considered for testing: Bcl2, IL7R, and MYC as down-regulated target genes; CSRP2, HEXIM1, and HIST1H2BK as up-regulated target genes.) A range of PD biomarkers will be explored in surrogate samples from all subjects treated, using appropriate assays to establish target engagement. Rather than rely on gene expression changes in cancer cells, these PD biomarkers will be based on current PD knowledge from translational studies of mouse and human whole blood (e.g. [Figure 3](#) below). Using RNA extracted from whole blood samples collected both prior to and following administration of MK-8628, messenger RNA transcript profiling may be performed to assess gene expression and evaluate whether changes in specific genes or sets

of genes may represent a PD biomarker of response. Potential limitations of this assay include subject-to-subject variability and a small effect size of induction or repression upon treatment with MK-8628. Due to these limitations, the PD endpoint is considered to be qualitative given the assay may not be able to differentiate target engagement between the MK-8628 doses examined in this study.

See [Figure 3](#). Whole blood from 6 normal healthy volunteers was treated with either vehicle (0.1% DMSO) or increasing concentrations of MK-8628. After 4 hours, whole blood was lysed (PAXgene tube) and mRNA extracted for qPCR analysis of candidate BET target genes. Data were normalized ( $\Delta Ct$ ) by PPIB and plotted for all six individuals as change in  $\Delta Ct$ .

[figure not shown]

Figure 3 Dose-Dependent Changes in BET Protein Target Gene Expression in Human Whole Blood Ex Vivo

#### 4.2.3.3 Efficacy Endpoints

##### 4.2.3.3.1 Secondary Efficacy Endpoints

The secondary efficacy objectives for this trial are to evaluate the anti-tumor activity of MK-8628 in subjects with AML (de Novo and post-MDS) and DLBCL biomarker unselected. Secondary efficacy endpoints include (1) ORR, defined per standard response criteria for acute leukemia (Section 12.4) and malignant lymphoma (Sections 12.5), as assessed by investigator, (2) DOR, defined as the time from first documented evidence of CR or PR until disease progression or death due to any cause, whichever occurs first, (3) disease control rate defined as the percentage of subjects with advanced or metastatic cancer who have achieved CR, PR and stable disease.

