#### 4.1.1.3 MK-8628 – Ongoing Clinical Trials in Hematologic Malignancies

Study MK-8628-001 (previously known as OTX015\_104), a Phase Ib study in subjects with AL or other hematologic malignancies was started (first subject enrolled) in January 2013. The study is composed of a dose escalation part evaluating MK-8628/OTX015 doses from 10 mg to 160 mg QD in subjects with AL or other hematologic malignancies using a classic 3+3 design, followed by evaluation of dose expansion cohorts in three selected hematologic indications with the QD dosing. The preliminary RD and schedule for the Phase 2 study in hematologic malignancies was 80 mg/day with 14 days on/7 days off schedule, with dose interruptions in the event of grade 4 thrombocytopenia. This preliminary RD will be further explored looking at 20 mg and 30 mg BID continuous dosing. Phase 1 expansion cohorts in AML de novo, AML post-MDS, and DLBCL at 80 mg (14 days on/7 days off) are ongoing. Consideration for further enrollment will be based on findings at additional BID continuous dosing. As of 04-Sep-2015, a total of 135 subjects have been enrolled.

Efficacy data is available for 135 subjects with advanced hematologic malignancies as of 04-Sep-2015. Of 75 subjects with AL, complete responses were observed for 2 subjects (1 subject in the 40 mg QD cohort and 1 subject in the 160 mg QD cohort) and a complete response with incomplete marrow recovery was observed for 1 subject. Of 48 subjects with lymphoma, a complete response was observed for 2 subjects (at 120 mg QD on 14-day and 21- day regimens) and a partial response was observed for 2 subjects (at 80 mg QD on 14-day and 21- day regimens); stable disease was observed for 18 subjects. Of 12 subjects with multiple myeloma, no responses were observed; stable disease was reported for 5 subjects. The duration of response among all responders ranged from 1.4 to 9.2 months.

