#### 7.1.2.7.2 Positron Emission Tomography (PET), Computed Tomography (CT), & Criteria for Response Assessment - DLBCL

The anti-tumor activity of MK-8628 will be evaluated as part of the efficacy endpoints using the following International Working Group criteria:

- 5 Point-Scale per the Lugano Classification (Cheson et al, *J Clin Oncol*, 2014) [46]  
See Appendices 12.5.

These International Working Group criteria will be applied by the site as the primary measure for assessment of disease response and as a basis for all protocol guidelines related to disease status (e.g. discontinuation of study therapy). The assessments will involve the use of PET-CT and CT imaging (PET based response to analyze FDG-avid uptake using a 5 point scale, and confirm residual vs. metabolically active tumor locations). The timing of tumor response assessments should follow calendar days and should not be adjusted for delays in cycle starts. The same imaging technique should be used in a subject throughout the trial. Local reading (investigator assessment with site radiology reading) will be used to determine eligibility and for subject management. The sponsor may potentially collect radiologic assessments for retrospective analysis by a central vendor. Assessment of lymphoma B symptoms should occur with each lymphoma disease response assessment.

The tumor response assessments should be completed at the following visits:

- \*Screening
- Cycle 5 day 1 (Week 12,  $\pm$  3 days) and every 12 weeks thereafter ( $\pm$  3 days)
- \*\* Treatment Discontinuation Visit
- \*\*\*Follow-up Visits (every 12 weeks post-treatment,  $\pm$  7 days)

\*Routine imaging (or bone marrow biopsy) performed outside of the scope of this study will be acceptable to complete the criteria for response assessment at screening, if performed  $\leq$  4 weeks prior to study entry.

\*\*In subjects with an unconfirmed PD assessment, a radiological assessment should be performed at the time of treatment discontinuation. If previous scan was obtained within 4 weeks prior to the date of discontinuation, then a repeat scan at treatment discontinuation isn't mandatory. However, imaging should occur at any time where there is clinical suspicion of progression.

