### 8.4.2 Efficacy/Pharmacokinetics/Pharmacodynamics Endpoints

Secondary efficacy endpoints are presented below:

**Objective Response Rate (ORR):** is defined as the percentage of subjects who have achieved confirmed complete response (CR) or partial response (PR) according to specified response criteria for each tumor type (AML or DLBCL) by the investigator review.

**Duration of Response (DOR):** is defined as the time interval between the date of the first confirmed response (CR/PR) (the response prior to confirmation) and the date of first documented disease progression based upon specified response criteria for each tumor type (AML or DLBCL) by the investigator review.

**Disease Control Rate (DCR):** is defined as the percentage of subjects who have achieved stable disease or confirmed complete response (CR) or confirmed partial response (PR) according to Response Evaluation Criteria in AML or DLBCL (see Section 7.1.2.7.1 and 7.1.2.7.2) by the investigator review. Subjects with missing response will be considered not to have achieved disease control.

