No response or stable disease	No metabolic response	Stable disease
Target nodes/nodal masses, extranodal lesions	Score 4 or 5 with no significant change in FDG uptake from baseline at interim or end of treatment	< 50% decrease from baseline in SPD of up to 6 dominant, measurable nodes and extranodal sites; no criteria for progressive disease are met
Nonmeasured lesions	Not applicable	No increase consistent with progression
Organ enlargement	Not applicable	No increase consistent with progression
New lesions	None	None
Bone marrow	No change from baseline	Not applicable
Progressive disease	Progressive metabolic disease	Progressive disease requires at least 1 of the following
Individual target nodes/nodal masses	Score 4 or 5 with an increase in intensity of uptake from baseline and/or	PPD progression
Extranodal lesions	New FDG-avid foci consistent with lymphoma at interim or end-of-treatment assessment	An individual node/lesion must be abnormal with: LD i > 1.5 cm and Increase by $\geq 50\%$ from PPD nadir and An increase in LD i or SD i from nadir 0.5 cm for lesions $\leq 2$ cm 1.0 cm for lesions $> 2$ cm In the setting of splenomegaly, the splenic length must increase by $> 50\%$ of the extent of its prior increase beyond baseline (eg, a 15-cm spleen must increase to $> 16$ cm). If no prior splenomegaly, must increase by at least 2 cm from baseline. New or recurrent splenomegaly.
Nonmeasured lesions	None	New or clear progression of preexisting nonmeasured lesions

Response and Site	PET-CT Based Response	CT-Based Response
New lesions	New FDG-avid foci consistent with lymphoma rather than another etiology (eg, infection, inflammation). If uncertain regarding etiology of new lesions, biopsy or interval scan may be considered.	Regrowth of previously resolved lesions A new node > 1.5 cm in any axis A new extranodal site > 1.0 cm in any axis; if < 1.0 cm in any axis, its presence must be unequivocal and must be attributable to lymphoma Assessable disease of any size unequivocally attributable to lymphoma
Bone marrow	New or recurrent FDG-avid foci	New or recurrent involvement

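### DCR accepts stable disease seen at any time, so before the Week 12 scan a DLBCL subject's DCR status depends on whether an off-schedule scan was taken

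*Combined protocol and SAP*

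**What the plan says.** DCR is a secondary efficacy endpoint (Section 3.2) and is defined twice. Section 4.2.3.3.1 has "disease control rate defined as the percentage of subjects with advanced or metastatic cancer who have achieved CR, PR and stable disease". Section 8.4.2, the operative SAP text, has "percentage of subjects who have achieved stable disease or confirmed complete response (CR) or confirmed partial response (PR"; the rest of that sentence only names the response criteria and the investigator as assessor. Confirmation is asked of CR and PR. Nothing is asked of SD. Section 8.4.2 then adds: "Subjects with missing response will be considered not to have achieved disease control".

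The response criteria in Section 12.5 (Table 14) do not supply a minimum time. In the CT column SD is a size change below the PR threshold where "no criteria for progressive disease are met". In the PET-CT column it is "Score 4 or 5 with no significant change in FDG uptake from baseline at interim or end of treatment". Either can be read from one scan against baseline.

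For DLBCL, Section 7.1.2.7.2 puts the first post-baseline scan at Cycle 5 Day 1 (Week 12, ±3 days), then every 12 weeks. Two routes lead to an earlier scan. One is a scan at discontinuation, which Section 7.1.2.7.2 and note h of the flow chart (Section 6.0) tie to subjects whose progression is unconfirmed and waive if there was a scan in the preceding 4 weeks. The other is open-ended: "However, imaging should occur at any time where there is clinical suspicion of progression".

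The efficacy population is everyone who took at least one dose (Section 8.5.2), so early stoppers stay in the denominator.

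**The concern.** A DLBCL subject on schedule has to remain free of progression for about 12 weeks before SD can be recorded. A subject who stops treatment at Week 3 and is scanned then has to remain so for about 3 weeks. Both count equally as disease control. The same Week 3 stopper without a scan, and with none later, has a missing response and counts as a failure. For subjects who stop before Week 12, the endpoint thus partly measures scanning practice.

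The discontinuation trigger adds to this. It is unclear whether a subject who stops purely for toxicity falls under the condition about unconfirmed progression, while Sections 5.8 and 7.1.4.1 ask in general terms for the final-visit examinations to be done. Sites could reasonably differ. At stake is a descriptive DCR whose value, and whose comparison between 20 mg and 30 mg BID, could shift for reasons unrelated to drug activity.

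**Working it through.** **1. The plan's own figures.** The documents give no figure for DCR. Section 8.6.2 specifies a Clopper-Pearson interval, as used in the last column of Table 11 (Section 8.9). Recomputing that column from beta quantiles reproduces all 11 rows to three decimals; 3/14, for example, gives (0.047, 0.508).

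**2. Timing.** Cycle 5 Day 1 = 4 × 21 + 1 = Day 85; 84/7 = 12.0 weeks, as stated. The window opens at 85 − 3 = Day 82. Section 7.1.2.7.2 ties assessments to calendar days regardless of cycle delays, so Day 82 is well defined.

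**3. Effect per subject.** Section 8.9 allows up to 14 DLT-evaluable subjects per dose level and 28 per tumour cohort. One early SD reading is worth 1/14 = 7.1 points or 1/28 = 3.6 points. (The treated denominator can be somewhat larger, because subjects not evaluable for DLT are replaced under Section 5.9; each step is then slightly smaller.) Assume, hypothetically, 3 of 14 or 6 of 28 controlled at Week 12 or later, plus k early stoppers with an SD scan:

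| k | DCR, n = 14 (95% CI) | DCR, n = 28 (95% CI) |
|---|---|---|
| 0 (equals the anchored DCR) | 21.4% (4.7–50.8) | 21.4% (8.3–41.0) |
| 1 | 28.6% (8.4–58.1) | 25.0% (10.7–44.9) |
| 2 | 35.7% (12.8–64.9) | 28.6% (13.2–48.7) |
| 3 | 42.9% (17.7–71.1) | 32.1% (15.9–52.4) |

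**4. Direction.** Assume exponential time to progression with median m weeks, S(w) = 0.5^(w/m); a share q of subjects stopping at Week 3; and a fraction f of those scanned at that point, the rest never scanned. Then

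DCR = (1 − q)·S(12) + q·f·S(3).

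With no early stops DCR = S(12). The two are equal when f = S(12)/S(3). For q I take 11.7% (7/60, discontinuation for any AE) and, as an upper illustration, 30% (18/60, Cycle 1 DLT). Both come from the non-acute-leukaemia subjects of MK-8628-001 (Section 4.1.1.3).

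| m | No early stops | q = 11.7%: all / none scanned | q = 30%: all / none scanned | Break-even f |
|---|---|---|---|---|
| 4 | 12.5% | 18.0% / 11.0% | 26.6% / 8.7% | 21% |
| 6 | 25.0% | 30.3% / 22.1% | 38.7% / 17.5% | 35% |
| 8 | 35.4% | 40.2% / 31.2% | 47.9% / 24.7% | 46% |
| 12 | 50.0% | 54.0% / 44.2% | 60.2% / 35.0% | 59% |

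For example, with m = 4, q = 0.117 and f = 1: 0.883 × 0.125 + 0.117 × 0.595 = 0.180. If all early stoppers are scanned, DCR rises by 4 to 14 points; if none is, it falls by 1.5 to 15 points. The drug effect is the same throughout.

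**5. How many early stops to expect.** At 7/60, 14 × 0.117 = 1.6 subjects per dose level. At 2/60 (drug-related AEs only, same section), 14 × 0.033 = 0.5, and the binomial chance of two or more is about 8%. Neither rate is limited to stops before Week 12.

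**The case against.** A reader might infer that toxicity at 30 mg BID will inflate its DCR and mislead the choice of RP2D. The documents do not support that.

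- **RP2D.** Section 5.2.1.3 makes a drug-related AE that stops treatment in Cycle 1 a DLT. Sections 4.2.3.1.1 and 5.2.1.4 say the DLT rate drives dose selection and the other facets are supportive. A stop that lifts DCR therefore also counts against that dose on the primary endpoint. DCR is not itself named as an RP2D input; only an early efficacy signal is.
- **Direction.** Unscanned stoppers lower DCR. The discontinuation scan is conditional, and the 4-week waiver could exempt stops up to about Day 14 even after a screening scan on Day −14. The other trigger, suspected progression, tends to select progressing subjects. Nothing in the documents says an early scan will usually read SD.
- **Size.** A reader might also take the MK-8628-001 lymphoma result (2 CR, 2 PR, and "stable disease was observed for 18 subjects" among 48, so 18 of 22 controlled subjects by SD) as evidence of early SD. It is not: it pools lymphomas, comes from other doses and schedules, and gives no scan timing. It shows only that SD can make up most of a DCR. The 30% share in the working is a DLT rate, not a stop rate; Table 5 mostly holds and resumes treatment.
- **Inference.** Section 8.3 states no hypotheses, and presentation by dose level is descriptive. For 4/14 the interval is already 8.4% to 58.1%.
- **Timing.** Section 1.0 ends enrolment and further efficacy recording.

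These limit the consequence; they do not remove the defect. The rule, followed exactly, still gives two subjects with the same course opposite results according to whether one was scanned. Section 1.0 does not withdraw the DCR analysis of data already collected, and Section 10.7 intends publication even after early termination.

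**Conclusion.** The point holds as a scoring defect in a descriptive secondary endpoint, and it should be fixed. Both DCR definitions accept SD at any time, Table 14 assigns it from a single scan, and missing counts as failure. Before Week 12, DCR status in a DLBCL early stopper therefore depends on whether an off-schedule scan exists. Each such subject is worth 7.1 points at n = 14 or 3.6 points at n = 28, and the net effect can be up or down.

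The per-subject figures are arithmetic on the planned numbers. The base counts, the values of k, the exponential model, the Week 3 stop and the borrowed stop shares are assumptions, so the 4 to 14 point rise and the corresponding fall are illustrations, not forecasts. Type I error and sample size are not affected, and any effect on the RP2D is limited.

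**What to change.** In Sections 4.2.3.3.1 and 8.4.2, or in the supplemental SAP or CSR analysis rules if the protocol text is no longer being amended, state for DLBCL:

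- SD counts toward DCR only if documented on a scan on or after Day 82 (Week 12 less its 3-day window) and before any new anticancer therapy.
- A subject without confirmed CR or PR whose only SD reading is earlier counts as not controlled.
- Whether SD first seen on a post-treatment follow-up scan counts. This must be explicit: a subject who stops at Week 3 and is followed every 12 weeks could be scanned at about Week 15, off drug, and would pass the Day 82 rule.
- Any-duration DCR is reported as a sensitivity analysis. The difference between the two rates shows how many subjects were controlled only by an early SD reading.

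Section 8.0 provides the supplemental SAP route for non-confirmatory changes before final database lock. If lock has passed, the CSR should label the rule post hoc. The cost is a few sentences and one extra line in the efficacy table. No new scans are needed. The downside is a slightly less favourable DCR.
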